#### **7.4.3. Laboratory and Other Safety Assessment Abnormalities Reported as AEs and SAEs**

Any abnormal laboratory test results (haematology, clinical chemistry, or urinalysis), or other safety assessments (e.g., ECGs, radiological scans, vital signs measurements) including those that worsen from baseline, and events felt to be clinically significant in the medical and scientific judgement of the investigator are to be recorded as an AE or SAE, in accordance with the definitions provided.

In addition, an associated AE or SAE is to be recorded for any laboratory test result or other safety assessment that led to an intervention, including permanent discontinuation of study treatment, dose reduction, and/or dose interruption/delay.

Any new primary cancer must be reported as an SAE.

However, any clinically significant safety assessments that are associated with the underlying disease, unless judged by the investigator to be more severe than expected for the subject's condition, are not to be reported as AEs or SAEs.

#### **7.4.4. Cardiovascular Events**

Investigators will be required to fill out event specific data collection tools for the following AEs and SAEs:

- Myocardial infarction/unstable angina
- Congestive heart failure
- Arrhythmias
- Valvulopathy
- Pulmonary hypertension
- Cerebrovascular events/stroke and transient ischemic attack
- Peripheral arterial thromboembolism
- Deep venous thrombosis/pulmonary embolism
- Revascularisation

This information should be recorded in the specific cardiovascular eCRF within one week of when the AE/SAE(s) are first reported.

#### **7.4.5. Death Events**

A specific death data collection tool is to be completed for all deaths, whether or not they are considered SAEs. The death data collection tool includes questions regarding cardiovascular (including sudden cardiac death) and non-cardiovascular death.

This information should be recorded within one week of when the death is first reported.

#### **7.4.6. Disease-Related Events and/or Disease-Related Outcomes Not Qualifying as SAEs**

An event which is part of the natural course of the disease under study (i.e., disease progression or hospitalization due to disease progression) does not need to be reported as an SAE.

Death due to disease under study is to be recorded on the Death eCRF form and does not need to be reported as SAE.

However, if the underlying disease (i.e., progression) is greater than that which would normally be expected for the subject, or if the investigator considers that there was a causal relationship between treatment with study medication(s) or protocol design/procedures and the disease progression, then this must be reported as an SAE.

#### **7.4.7. Time Period and Frequency of Detecting AEs and SAEs**

The investigator or site staff is responsible for detecting, documenting and reporting events that meet the definition of an AE or SAE.

AEs will be collected from the time of treatment with the first dose of octreotide for subjects randomised to receive octreotide and treatment with the first dose of lapatinib and capecitabine for subjects randomised to receive no octreotide until 30 days following the end of the 24 week study period or discontinuation of study-related treatment, whichever is sooner, regardless of initiation of a new cancer therapy or transfer to hospice.

Serious AEs will be collected over the same time period as stated above for AEs. In addition, any SAE assessed **as related** to study participation (e.g., protocol-mandated procedures, invasive tests, or change in existing therapy), study treatment or GSK concomitant medication must be recorded from the time a subject consents to participate in the study up to and including any follow-up contact. All SAEs will be reported to GSK within 24 hours, as indicated in Section 7.4.9.

Serious AEs, AEs of special interest, AEs leading to treatment discontinuation and pregnancies will be collected for all subjects who enter the LTFU phase of the study (Section 7.1.9).

After discontinuation of study treatment, the investigator will monitor all AEs/SAEs that are ongoing until resolution or stabilization of the event or until the subject is lost to follow-up. At any time after 30 days the investigator may report any AE that they believe possibly related to study treatment.

#### **7.4.8. Method of Detecting AEs and SAEs**

Care must be taken not to introduce bias when detecting AEs and/or SAEs. Open-ended and non-leading verbal questioning of the subject is the preferred method to inquire about AE occurrence. Appropriate questions include:

“How are you feeling?”

“Have you had any (other) medical problems since your last visit/contact?”

“Have you taken any new medicines, other than those provided in this study, since your last visit/contact?”

#### **7.4.9. Prompt Reporting of SAEs and Other Events to GSK**

SAEs, pregnancies, and liver function abnormalities and any other events meeting pre-defined criteria will be reported promptly by the investigator to GSK as described in Table 20 once the investigator determines the event meets the protocol definition for that event.

**Table 20 Adverse events to be reported promptly to the study sponsor**

Type of Event	Time Frame	Documents	Time Frame	Documents
All SAEs	24 hours	SAE data collection tool	24 hours	Updated SAE data collection tool
CV events or death	Initial and follow up reports to be completed within one week of when the cardiovascular event or death is reported	“CV events” and/or “death” data collection tool(s) if applicable	Initial and follow up reports to be completed within one week of when the cardiovascular event or death is reported	Updated “CV events” and/or “death” data collection tool(s) if applicable
Pregnancy	2 Weeks	Pregnancy Notification Form	2 Weeks	Pregnancy Follow up Form
Liver chemistry abnormalities Phase II:				
ALT $\geq$ 3xULN and bilirubin $\geq$ 2xULN (>35% direct) (or ALT $\geq$ 3xULN and INR>1.5, if INR measured) 	24 hours 	SAE data collection tool. Liver Event Case Report Form (CRF) and liver imaging and/or biopsy CRFs if applicable 	24 hours	Updated SAE data collection tool. Updated Liver Event CRF 
ALT $\geq$ 5xULN; ALT $\geq$ 3xULN with hepatitis or rash or 3xULN $\geq$ 4 weeks	24 hours 	Liver Event CRF 	24 hours	Updated Liver Event CRF 
ALT $\geq$ 3xULN and <5xULN and bilirubin <2xULN	24 hours 	Liver Event CRF does not need completing unless elevations persist for 4 weeks or subject cannot be monitored weekly for 4 weeks 		

1. GSK to be notified at onset of liver chemistry elevations to discuss subject safety.
2. Liver Event Documents (i.e., “Liver Event CRF” and “Liver Imaging CRF” and/or “Liver Biopsy CRF”, as applicable) should be completed as soon as possible
3. .INR measurement is not required; if measured, the threshold value stated will not apply to subjects receiving anticoagulants.

Liver chemistry stopping criteria are described in Section 5.13.1.

Methods for detecting, recording, evaluating, and following up on AEs and SAEs and procedures for completing and transmitting SAE reports to GSK are provided in the SPM. Procedures for post-study AEs and SAEs are provided in the SPM.

#### **7.4.10. Regulatory Reporting Requirements for SAEs**

Prompt notification of SAEs by the investigator to GSK is essential so that legal obligations and ethical responsibilities towards the safety of subjects are met.

GSK has a legal responsibility to notify both the local regulatory authority and other regulatory agencies about the safety of a product under clinical investigation. GSK will comply with country specific regulatory requirements relating to safety reporting to the regulatory authority, Institutional Review Board (IRB)/Independent Ethics Committee (IEC) and investigators.

Investigator safety reports are prepared for suspected unexpected serious adverse reactions according to local regulatory requirements and GSK policy and are forwarded to investigators as necessary.

An investigator who receives an investigator safety report describing a SAE(s) or other specific safety information (e.g., summary or listing of SAEs) from GSK will file it with the Investigator Brochure and will notify the IRB/IEC, if appropriate according to local requirements.

### **7.5. Pregnancy Testing, Prevention and Reporting**

#### **7.5.1. Pregnancy Test and Prevention**

The need for a screening pregnancy test depends on whether a female subject is of childbearing potential or non-childbearing potential.

**A female of non-childbearing potential** (i.e., physiologically incapable of becoming pregnant) is defined as any female who has had a hysterectomy, bilateral oophorectomy (ovariectomy) or bilateral tubal ligation, or is post-menopausal with total cessation of menses for at least 1 year.

A practical definition accepts menopause after 1 year without menses with an appropriate clinical profile, e.g., age appropriate, >45 years in the absence of hormone replacement therapy. In questionable cases, the subject must have a follicle stimulating hormone value >40 mIU/mL and an oestradiol value < 40pg/mL (<140 pmol/L).

**A female of child-bearing potential** is defined as any female who does not meet the criteria of non-childbearing potential as described in the previous paragraph.

If a female subject is of childbearing potential, she must have a serum  $\beta$ -hCG pregnancy test performed within 7 days prior to treatment with octreotide if randomised to receive octreotide or the first dose of lapatinib with capecitabine if randomised to receive no octreotide, but preferably as close to the start of treatment as possible. Subjects with a

positive pregnancy test result must be excluded from the study. Subjects with a negative pregnancy test result must agree to use an effective contraception method as described below during the study until 30 days following the end of the 24 week study period or until 30 days following the last dose of lapatinib and capecitabine for subjects who enter the LTFU phase of the study. Subjects who continue treatment with lapatinib and capecitabine beyond the 24 week study period but do not enter the LTFU phase of the study should continue to use an acceptable contraceptive method in accordance with the Lapatinib and Capecitabine SPCs.

GSK acceptable contraceptive methods, when used consistently and in accordance with both the product label and the instructions of the physician, are as follow:

- An intrauterine device with a documented failure rate of less than 1% per year.
- Vasectomised partner who is sterile prior to the female subject's entry and is the sole sexual partner for that female.
- Complete abstinence from sexual intercourse for 14 days prior to first dose of study-related treatment, through the dosing period, and for at least 30 days following the end of the 24 week study period or until 30 days following the last dose of lapatinib and capecitabine for subjects who enter the LTFU phase of the study.  
**UK subjects:** In the UK, sexual inactivity by abstinence must be consistent with the preferred and usual lifestyle of the subject. Periodic abstinence (e.g. calendar, ovulation, symptothermal, postovulation methods) and withdrawal are not acceptable methods of contraception.
- Double-barrier contraception: condom and occlusive cap (diaphragm or cervical/vault caps) with a vaginal spermicidal agent (foam/gel/cream/suppository).
- Implants of levonorgestrel where not contraindicated for this subject population or per local practice.
- Injectable progesterone where not contraindicated for this subject population or per local practice.
- Oral contraceptives (either combined or progesterone only) where not contraindicated for this subject population or per local practice.

Female subjects who are lactating must discontinue nursing prior to the first dose of study treatment and must refrain from nursing throughout the treatment period and 30 days following the end of the 24 week study period or until 30 days following the last dose of lapatinib and capecitabine for subjects who enter the LTFU phase of the study. Subjects who continue treatment with lapatinib and capecitabine beyond the 24 week study period but do not enter the LTFU phase of the study should discontinue nursing in accordance with the Lapatinib and Capecitabine SPCs.

## **7.5.2. Pregnancy Reporting**

Any pregnancy that occurs during study participation must be reported using a clinical trial pregnancy form. To ensure subject safety, each pregnancy must be reported to GSK within 2 weeks of learning of its occurrence. The pregnancy must be followed up to determine outcome (including premature termination) and status of mother and child. Pregnancy complications and elective terminations for medical reasons must be reported as an AE or SAE. Spontaneous abortions must be reported as an SAE.

Any SAE occurring in association with a pregnancy brought to the investigator's attention after the subject has completed the study and considered by the investigator as possibly related to the study treatment, must be promptly reported to GSK.

## **7.6. Laboratory Assessments**

All laboratory assessments will be performed by a local laboratory. Prior to administration of the first dose of study drug, results of laboratory assessments should be reviewed. Any laboratory test with a value outside the normal range may be repeated (prior to the first dose) at the discretion of the investigator. A subject with a laboratory value outside the reference range(s) or ranges for tests which relate to inclusion criteria (Section 4.1.2) and exclusion criteria (Section 4.1.3), the contraindications, special warnings and precautions for use, and other information included in the Lapatinib, Capecitabine and Octreotide SPCs may be included only if the investigator and GSK Medical Monitor agree that it is unlikely to introduce additional risk factors and will not interfere with study procedures.

All laboratory tests with values that are significantly abnormal during participation in the study or within 30 days following the end of the 24 week study period or until 30 days following the last dose of lapatinib and capecitabine for subjects who enter the LTFU phase of the study should be repeated until the values return to normal or baseline. If such values do not return to normal within a period judged reasonable by the investigator, the etiology should be identified and the sponsor notified.

## **7.7. Health Outcomes**

### **7.7.1. Health Outcomes Endpoints**

The health outcome endpoint of this study is subject-reported quality of life.

[figure not shown]
### **7.7.2. Health Outcomes Assessments**

Quality of life will be assessed using the FACIT-D ([Appendix 2](#)). Detail concerning the methods of collecting and returning FACIT-D data are included in the SPM.

All subjects will complete the baseline FACIT-D prior to randomisation, before any study related treatment is administered. Subjects randomised to receive treatment with octreotide will also complete the FACIT-D immediately before receiving the first dose of

lapatinib and capecitabine. All subjects will complete the FACIT-D every three weeks during treatment with lapatinib plus capecitabine through to withdrawal from the study or the end of the 24 week period of treatment with lapatinib and capecitabine, whichever is sooner.

The FACIT-D (version 4; [Appendix 2](#)) consists of the FACT-G [[Webster, 2003](#)] and a diarrhoea-specific subscale, and measures multidimensional quality of life in subjects with cancer. FACT-G includes 27 general questions relating to four subscales, PWB, SWB, EWB and FWB, and the DSS includes 11 questions. Subjects assess how true each statement has been for them in the previous 7 days on a 5-point scale ranging from 0 (not at all) to 4 (very much). Higher scores on the FACIT-D scales indicate a better quality of life. In psychometric testing, the FACT/FACIT system has shown good test-retest reliability and sensitivity to change when compared with ECOG performance status. The FACIT-D has been translated and validated in many languages, and the translations have been shown to have cross-cultural acceptability.

## 8. DATA MANAGEMENT

For this study subject data will be entered into GSK defined eCRFs, transmitted electronically to GSK or designee and combined with data provided from other sources in a validated data system.

Management of clinical data will be performed in accordance with applicable GSK standards and data cleaning procedures to ensure the integrity of the data, e.g., removing errors and inconsistencies in the data. AEs and concomitant medications terms will be coded using MedDRA and an internal validated medication dictionary, GSKDrug. Electronic CRFs (including queries and audit trails) will be retained by GSK, and copies will be sent to the investigator to maintain as the investigator copy.

The PRO data (FACIT-D and DMD) will be entered in a non-GSK database. This database will be used for the sole purpose of the LAP117314 study. Only authorised personnel will have access to the PRO database, and all personnel are obliged to fully comply with The Data Protection Act 1998. All electronic PRO data will be kept in a dedicated database in a secure data vault, on a dedicated database server. Access to the database will be password and access right controlled.

In all cases, subject initials will not be collected or transmitted to GSK in accordance with GSK policy.

## 9. DATA ANALYSIS AND STATISTICAL CONSIDERATIONS

### 9.1. Hypotheses

The primary objective of this study is to evaluate and compare whether administering prophylactic octreotide vs. no prophylactic octreotide reduces the incidence of cancer treatment-associated diarrhoea in subjects taking lapatinib plus capecitabine.

The study is designed to provide evidence to support the null hypothesis  $H_0: \delta \geq 0$  or to reject it in favour of the alternative hypothesis  $H_A: \delta < 0$ , where  $\delta$  is the difference in the incidence of Grade 2 or higher diarrhoea between prophylactic octreotide vs. no prophylactic octreotide.

### 9.2. Study Design Considerations

#### 9.2.1. Sample Size Assumptions

It is planned that a total of 140 subjects will be randomised in a 1:1 ratio i.e. 70 subjects in each treatment arm. LAP117314 is an exploratory Phase II study, and the sample size is not based on the number of subjects required to achieve a statistically significant pre-specified reduction in the control incidence of diarrhoea.

The overall incidence of diarrhoea associated with treatment with lapatinib and capecitabine ranges from less than 40% to more than 80% across a number of studies (Section 1.1). Only limited data are available on the incidence of diarrhoea with a severity of Grade 2 or more which can be used as a basis for sample size estimation. It is likely that the implementation of active diarrhoea management guidelines will limit the incidence of more severe diarrhoea which develops as a progression from inadequately treated mild diarrhoea. Therefore, a conservative approach has been taken in LAP117314, and data from study EGF111438, which shows the lowest incidence of diarrhoea with a severity of Grade 2 or more (20%), has been used as the basis for the power calculations. In addition, power calculations have been conducted based on a less conservative approach using data from EGF100151, in which diarrhoea management guidelines were not implemented and in which the incidence of diarrhoea with a severity of Grade 2 or more was 32%.

#### 9.2.2. Sample Size Sensitivity

Based on the results of EGF111438, an incidence of 20% of Grade 2 or higher diarrhoea is assumed for subjects who receive lapatinib and capecitabine with no prophylactic octreotide. The power for the analysis to detect a reduction in the incidence of Grade 2 or higher diarrhoea from 14% to 8% ranges from 69% to 25%, if the assumed incidence in the control arm is 20%, using a one-sided test with an alpha level of 0.025 (Table 21).

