circulating concentration is achieved. The standard starting dose of octreotide LAR is 20mg; the dose of octreotide LAR used in LAP117314 is 40mg, to ensure clinically relevant circulating concentrations of octreotide will be achieved in most subjects within 7 days after dosing, and to minimise the delay before starting treatment with lapatinib and capecitabine.

The efficacy of octreotide in the prevention of diarrhoea associated with treatment with lapatinib and capecitabine is unknown. Octreotide-associated gastrointestinal AEs are common, and could potentially worsen the overall incidence of diarrhoea and other AEs in subjects who receive octreotide LAR together with lapatinib and capecitabine. An independent SRT will review safety data in this study on an ongoing basis, in order to protect subjects' interests and to ensure their safety (Section 10.8). There are no pre-specified stopping criteria in LAP117314, but the SRT can recommend changes to the study protocol to ensure the subjects' safety if necessary.

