Diarrhoea, nausea and vomiting, dermatological events, hepatobiliary, cardiovascular and respiratory events have been identified as events of special interest relating to lapatinib. Management of dermatological events, gastrointestinal events, and cardiovascular and respiratory events is described in Section 5.12.1, Section 5.12.2, and Section 5.12.3, respectively. Dose delay and dose reduction guidance for lapatinib related to these events and to hepatobiliary events is described in Section 5.10. If future changes are made to this guidance, formal documentation will be created and stored with the study file. Any changes will be communicated to the investigative sites in the form of a letter and the revised version of the AE management or dose modification guidelines will be included in the SPM.

Hand and foot syndrome has been identified as an event of special interest relating to capecitabine. Management of this event is described in further detail in Section 5.12.4. Dose delay and dose reduction guidance for capecitabine related to this event is described in Section 5.11. If future changes are made to this guidance, formal documentation will be created and stored with the study file. Any changes will be communicated to the investigative sites in the form of a letter and the revised version of the AE management or dose modification guidelines will be included in the SPM.

There are no events of special interest relating to octreotide [[Octreotide SPC](#)].

The GSK SRT will review safety data from this study on an ongoing basis. A formal review of safety data will be conducted after the first 60 subjects (approximately 30 in each treatment arm) have received at least 9 weeks of treatment with lapatinib and capecitabine; subsequent reviews will be conducted at least every 12 weeks, or more frequently if required. It is anticipated that the SRT will meet at least three times during the course of the study. There are no pre-defined stopping rules for this study.

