#### **9.3.4. Interim Analysis**

An interim analysis will be conducted to assess the futility of octreotide in relation to reducing the incidence of Grade 2 diarrhoea after 9 weeks of treatment. This analysis will take place when at least 60 subjects have been randomised to treatment and completed their 9 week assessment. At this analysis a review of both the accumulating safety and efficacy data will be conducted by an independent review committee to assure the safety of the patients in the trial and to provide an opportunity to terminate the study if:-

- There is overwhelming clinical evidence of a negative imbalance in the safety profile of either treatment group
- There is not sufficient evidence of an effect of efficacy in the reduction of Grade 2 diarrhoea as described by the stopping rules in Section 9.3.4.2.

The independent review committee will review the accumulating safety data and also the analysis of the primary endpoint, the incidence of Grade 2 diarrhoea. There will be full treatment disclosure at the interim analysis to the Senior Management team, but the study team will remain blinded to treatment assignment and the results of the interim analysis.

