##### **9.3.4.2. Futility Analysis of Primary Endpoint**

A futility analysis of the incidence of Grade 2 diarrhoea, the primary endpoint, comparing this incidence between the group of subjects who receive lapatinib and capecitabine to the group of subjects who receive no prophylactic octreotide will be performed. This will take place at a single interim analysis after approximately 40% of subjects (60 subjects) have had at least 9 weeks of study treatment.

Early termination of the study will be considered by the independent review committee. Their recommendation will be based on the following points:-

- Whether it would be possible to draw any meaningful conclusions if the study were to continue to planned completion given the:-

- The clinical relevance of the observed incidence of Grade 2 diarrhoea.
- The conditional power based on data from approximately 40% of the patients
- The totality of the evidence observed.

For example:

- If the diarrhoea rate is 30% in the control arm, in order for the conditional power (under the current trend) to be around 50% to see a positive result at the end of the trial, we would need to see a diarrhoea rate of 16% or lower in the octreotide arm. (Equating to a difference in 14% in incidence between treatment arms)
- If the diarrhoea rate is 20% in the control arm, in order for the conditional power (under the current trend) to be around 70% to see a positive result at the end of the trial, we would need to see a diarrhoea rate of 6% or lower in the octreotide arm. (Equating to a difference of 14% in incidence between treatment arms)

The conditional power will need to be re-calculated based on the actual incidence and actual percentage of patients evaluated at the time of the interim analyses.

It is envisaged that if at least a modest improvement in the diarrhoea rate in the octreotide arm is not seen with a conditional power of at least 50% at the interim analysis, it is unlikely that the trial would justify octreotide use in clinical practice. Further confidence intervals around the estimate of the observed difference in incidence of Grade 3 diarrhoea will be provided to aid clinical judgement.

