2.9 Interim analysis

It was planned to have one formal interim analysis. The results were reviewed by the independent DMC. Based on the interim analysis DMC meeting (09-Sep-2016) it was recommended to stop the trial for futility.

3 Sample size calculation

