3.2 Sample Size Sensitivity

Based on the results of EGF111438, an incidence of 20% of Grade 2 or higher diarrhoea is assumed for subjects who receive lapatinib and capecitabine with no prophylactic octreotide. The power for the analysis to detect a reduction in the incidence of Grade 2 or higher diarrhoea from 14% to 8% ranges from 69% to 25%, if the assumed incidence in the control group is 20%, using a one-sided test with an alpha level of 0.025 ([Table 3-1](#)).

Table 3-1 Sensitivity of sample size based on 20% control incidence of Grade 2 or more diarrhoea

Incidence, no prophylactic octreotide	20%	20%	20%	20%	20%
Incidence, prophylactic octreotide	6%	7%	8%	10%	12%
Estimated Statistical Power	69%	61%	53%	37%	25%
Subjects per Treatment group	70	70	70	70	70

Based on the results of EGF100151, an incidence of 32% of Grade 2 or higher diarrhoea is assumed for subjects who receive lapatinib and capecitabine with no prophylactic octreotide. The power for the analysis to detect a reduction in the incidence of Grade 2 or higher diarrhoea from 20% to 12% ranges from 82% to 36%, if the assumed incidence in the control group is 32%, using a one-sided test with an alpha level of 0.025 ([Table 3-2](#)) [Table 3-2](#).

Table 3-2 Sensitivity of sample size based on 32% control incidence of Grade 2 or more diarrhoea

Incidence, no prophylactic octreotide	32%	32%	32%	32%	32%
Incidence, prophylactic octreotide	12%	14%	16%	18%	20%
Estimated Statistical Power	82%	72%	60%	48%	36%
Subjects per Treatment group	70	70	70	70	70

Power calculations were performed using nQuery software version 7.0.

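### The power tables ignore the futility look added by Amendment 2; always following its 50% conditional-power guideline costs 7 to 14 points of power, and the protocol does not settle whether it binds

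*Protocol*

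**What the plan says.** Protocol 9.2.2 (Tables 21 and 22) gives power for 70 subjects per arm at one-sided alpha 0.025. For a 20% control incidence, power to detect a reduction "from 14% to 8% ranges from 69% to 25%, if the assumed incidence in the control arm is 20"%. The 14% and 8% are absolute reductions: 20% to 6%, and 20% to 12%. For a 32% control incidence the tabulated range is 82% to 36%. Neither table mentions an interim analysis. SAP 3.2 repeats the figures: "from 14% to 8% ranges from 69% to 25%, if the assumed incidence in the control group is 20"%.

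Amendment 2 added a single futility look after about 60 subjects have had nine weeks of treatment. Section 9.3.4.2 says that "Early termination of the study will be considered by the independent review committee", on the basis of clinical relevance, conditional power and the totality of the evidence. It then envisages that the trial is unlikely to justify octreotide use in practice if at least a modest improvement "in the octreotide arm is not seen with a conditional power of at least 50% at the interim analysis".

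On whether this is a rule, Section 9.3.4 allows termination "as described by the stopping rules in Section 9.3.4.2". Section 3.1 says "There are no pre-defined stopping rules for this study" and Section 1.3.1 says "There are no pre-specified stopping criteria in LAP117314". SAP 2.9 records that at this look "it was recommended to stop the trial for futility".

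**The concern.** A futility look that can end the trial gives up some power, because some trials that would have succeeded at 140 subjects are stopped at 60. A 50% bar under the current trend is demanding when less than half the data are in. The power tables predate the look, and Section 9.2 is not among the changes listed for Amendment 2 in Appendix 8. A reader would take 69% or 82% as the chance of success for the largest effects in the amended design.

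At stake is how a futility stop is read. Neither document gives the probability of stopping when octreotide works as well as the tables suppose, and the protocol's statements on the status of the 50% bar conflict. The look had consequences, since the trial stopped there, although the SAP does not say which bar was applied.

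**Working it through.** **Inputs.** 70 per arm, one-sided alpha 0.025 and the incidences in Tables 21 and 22 (Protocol 9.2.1, 9.2.2); chi-square final test (9.3.5.1.1); interim at 60 subjects, current-trend conditional power, 50% bar (9.3.4.2). Assumed: 30 per arm at the look, no continuity correction, and no effect of imputation for withdrawals.

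**Step 1: reproduce the printed power.** For control rate p1, octreotide rate p2, pooled rate p = (p1 + p2)/2 and n = 70, the usual approximation is

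power = Φ{[(p1 − p2) − 1.96 √(2p(1−p)/n)] / √[(p1(1−p1) + p2(1−p2))/n]}.

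It gives 69.6, 61.6, 53.5, 38.0 and 25.1% for Table 21 (printed 69, 61, 53, 37, 25) and 82.2, 72.0, 60.3, 48.1 and 36.5% for Table 22 (printed 82, 72, 60, 48, 36). The tables are therefore fixed-design power with no interim.

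**Step 2: turn the guideline into a boundary.** With t = 30/70 = 0.429 and interim statistic z,

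conditional power = Φ[(z/√t − 1.96)/√(1 − t)].

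This reaches 50% when z = 1.96 × √0.429 = 1.283. As a check on the formula, the protocol's example of 30% v 16% gives z = 1.288 and conditional power 50.4%, matching its figure of around 50%. Its other example, 20% v 6%, gives 74.7% against a stated figure of around 70%.

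**Step 3: power with the guideline always followed.** Exact binomial enumeration of both stages (30 then 40 more per arm): continue if interim z ≥ 1.283, and reject if the final Pearson z ≥ 1.96 in favour of octreotide.

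| Control v octreotide | Printed power | Exact, no interim | Exact, guideline followed | Probability of stopping |
|---|---|---|---|---|
| 20 v 6% | 69% | 71.7% | 56.6% | 34.1% |
| 20 v 7% | 61% | 63.0% | 48.5% | 40.0% |
| 20 v 8% | 53% | 54.3% | 40.8% | 45.6% |
| 20 v 10% | 37% | 38.2% | 27.6% | 56.1% |
| 20 v 12% | 25% | 25.0% | 17.6% | 65.3% |
| 32 v 12% | 82% | 83.5% | 69.1% | 25.0% |
| 32 v 14% | 72% | 73.3% | 58.0% | 33.2% |
| 32 v 16% | 60% | 61.4% | 46.7% | 41.5% |
| 32 v 18% | 48% | 48.9% | 35.9% | 49.8% |
| 32 v 20% | 36% | 37.1% | 26.4% | 57.7% |

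Against the printed values the loss runs from 25 − 17.6 = 7.4 points to 72 − 58.0 = 14.0 points. Exact against exact it is 7.5 to 15.2 points.

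**Step 4: sensitivity.**
- At 31 per arm (62 were enrolled, SAP 1), power with the guideline is 56.9/48.6/40.8/27.3/17.2% and 68.2/57.3/46.2/35.7/26.4%, less than one point from the values above.
- At 28 per arm (exactly 40% of 140), the loss against print is 8.3 to 15.9 points.
- With a looser 40% bar at 30 per arm, power is 59.8% for 20 v 6% and 72.1% for 32 v 12%, about 9 and 10 points below print.
- With no effect (20 v 20% or 32 v 32%), 89.2% of trials stop and 1.6% reject.

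**Step 5: the examples as whole counts.** With 9/30 control events, 4/30 on octreotide gives conditional power 72% and 5/30 gives 45%. With 6/30, 2/30 gives 68% and 3/30 gives 34%. At the 50% level the most events allowed on octreotide are therefore 4 and 2.

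**The case against.** The strongest reply is that nothing printed is wrong. The tables are correct for a fixed design, and power without the interim is a legitimate figure to tabulate when the futility guideline is discretionary. Section 9.3.4.2 is discretionary in tone: termination is considered, the bar is envisaged, and the committee weighs the totality of the evidence. This stands as far as it goes. The loss calculated here is the always-followed case, and it is zero if the bar is never acted on. It does not remove the need for a label, because the protocol never calls the guideline non-binding and elsewhere calls it stopping rules.

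The statements in 1.3.1 and 3.1 that no stopping rules exist sit in paragraphs on safety review, so they may have been meant only for safety. Both are worded for the whole study, however, and a reader cannot tell.

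Operating characteristics may also have been given to the committee in an interim reporting plan, which Section 5.6 foresees and which is not among the documents reviewed. That is possible; the point here is only that the protocol and SAP do not give them.

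Finally, the study is declared exploratory, its size is not derived from a target reduction, and it has already stopped. That limits the consequence but not the mismatch between the tables and the amended design.

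**Conclusion.** The point holds. Tables 21 and 22, and SAP Tables 3-1 and 3-2, describe a design without the interim. With the 50% guideline always followed at 30 per arm, power is 7.4 to 14.0 points below the printed figures (7.5 to 15.2 exact against exact). The two largest tabulated effects would be stopped for futility about one time in three and one time in four. The size rests on 30 per arm at the look, an uncorrected chi-square test, a hard cut at 50% and no effect of imputing withdrawals. Partial adherence to the guideline would put the loss between zero and these values.

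The status of the guideline is unresolved: Section 9.3.4 conflicts with 1.3.1 and 3.1, and 9.3.4.2 does not say whether it binds. Type I error falls rather than rises, and the endpoint, test and estimate are untouched. This should be corrected, but its consequence is limited in an exploratory trial that has ended.

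**What to change.** 1. Head Protocol Tables 21 and 22 and SAP Tables 3-1 and 3-2 as power without the interim analysis. Add two rows to each: probability of stopping at the interim, and power with the 50% guideline followed.
2. State in 9.3.4.2 whether the guideline is binding or non-binding, and reconcile 1.3.1, 3.1 and 9.3.4 with that statement.
3. Optionally, give both examples in 9.3.4.2 as attainable counts at the same 50% level: at most 4/30 on octreotide against 9/30 control events, and at most 2/30 against 6/30.
4. Optionally, mark SAP Section 3 as the original plan, since enrolment ended at 62.

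The cost is a heading, two table rows and a sentence on binding status, together with the matching edits in 1.3.1, 3.1 and 9.3.4. The with-guideline power looks less favourable. No extra patients are needed and no analysis changes.
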